Appendix C – Interview Guide	

#### Outline

- Existing research shows strong link between asthma patient-relevant outcomes and anxiety Mindfulness has been shown to be effective but 'classic' mindfulness courses are challenging to deliver.
- We have secured support from 'Headspace' to deliver a stress-reduction digital mindfulness course to 80 patients with asthma (vs. 40 control patients), with access to usage data. Headspace will supply access to their product to all participants for the duration of the study free of charge.
- Our feasibility study will quantitatively examine recruitment, retention and response rate to the Headspace intervention and the degrees to which these differ from the in-person mindfulness intervention delivered in the MIDAS study (SPCR ref: 273) as well as exploring measures of quality of life, mood (anxiety/depression) and asthma control.
- Qualitative outcomes will include the extent to which a stress-reduction based intervention is appropriate for a chronic health condition.
- [name] has secured NIHR SPCR Translational Fellowship to cover salary and NIHR SPCR grant to cover research costs. NIHR CRN: Wessex will provide service support costs as appropriate.

#### Aim

To determine the feasibility and estimate effectiveness of Headspace, a digital mindfulness-based stress-reduction app, in patients with sub-optimally controlled asthma.

# Lay Summary

Mindfulness is a type of meditation-based therapy that has been used to treat a range of health conditions, most commonly mood-disorders such as anxiety and depression. To date, few studies have explored how mindfulness can help chronic health conditions such as asthma. In a previous study we looked at how acceptable a traditional 'short-course' of mindfulness could help patients with difficult asthma. Patients liked the mindfulness and felt it helped how they felt about their asthma, but attendance was low (perhaps because of the commitment of attending a weekly group meeting). We want to see if 'Headspace', a mindfulness-based 'online' programme that can be accessed by app or website, can help. The Headspace programme takes 30 days of 10-minute practices that can be done whenever it is convenient for the user. Because this is a feasibility study, we will mainly be looking at how many people want to take part in the study, how many go on to take part and how many complete the whole study.

The study will take questionnaire measures of mood and asthma-related quality of life in patients with asthma, before and after using Headspace. Change in these 80 patients will be compared to a control group of 40 patients who will receive their usual care from their GP team. Headspace have allowed free access to their intervention to all participants in the study (although the control group will only be given access after they have given their follow-up measures). Should they wish, participants in both groups will be able to request an additional 6-months of free access to Headspace at the end of the study .We will also call some of the participants and ask them questions about their experience of the study and of using Headspace, and how they think Headspace (and mindfulness more broadly) could help their asthma. This study will help us to design an online programme specifically for people with asthma, to improve their quality of life beyond what can be offered by 'pharmacological' treatments such as new medication types.

## Summary

We are examining the use of 'mindfulness' training for people with poorly controlled asthma (PCA) and anxiety. Mindfulness focuses on managing bodily sensations in a calm and accepting way. Participants pay particular attention to breathing patterns. Mindfulness interventions have shown to help in anxiety, depression and chronic pain, but have had little attention in asthma. Recent research has suggested that mindfulness training can offer benefits to patients with asthma Significant anxiety is six times as common in people with asthma, particularly when control is poor . Having attacks of breathlessness can be frightening, increases anxiety levels even in stable and well-adjusted people with asthma, and some may become clinically anxious or depressed with evidence that the presence of psychiatric co-morbidity accounted for 29% of variation in asthma control.

Mindfulness practice involves purposeful, non-judgemental attention to and acceptance of experiences. This differs from interventions such as cognitive behaviour therapies, which seek to identify and correct maladaptive thoughts/behaviours . A recent comprehensive meta-analysis of 209 studies has shown that mindfulness-based therapy is an effective treatment for a variety of psychological problems and is especially effective for reducing anxiety, depression and stress. Recent cognitive-affective models have suggested that such maladaptive thoughts may underly symptom perception and contribute to the etiology and maintenance of asthma . Recently, a single small (N=83) US study investigated 8 weeks of mindfulness training in PCA in a group of patients with asthma, with patients showing clinically significant improvements in QoL and perceived stress (vs. educational control program, *ps* < .001) . Mindfulness is often delivered in 'mindfulness-based stress reduction' (MBSR) courses that require attendance to 8-weekly sessions, with daily homework practice and a full-day retreat. This study did however report great difficulty in both recruiting and retaining patients,

indicating that alternative and more convenient ways of delivering mindfulness training may be more acceptable and useful for the majority of asthma sufferers.

The full traditional mindfulness training programme is often challenging for patients to complete - previous research (SPCR FR9: 273) has examined the feasibility of mindfulness training to patients attending the 'difficult asthma' clinic in Southampton. In focus groups patients reported (improvements in subjective anxiety, increased relaxation, improved breathing control). However, there were a number of methodological challenges presented even by the reduced 4-week (one session/week of approx. 1 hr) group mindfulness training, including difficulty recruiting patients due to lack of time to and willingness to attend practice sessions.

Digital interventions can reach populations with long-term conditions without requiring face-to-face contact, with positive effects reported across a range of guided practices (i.e. pre-recorded), allowing convenience to patients in terms of timing and situation. Such interventions, if clinically effective, are likely to be cost-effective due to the low associated delivery costs. Headspace is the highest-rated mindfulness-based app and has shown benefits in reducing anxiety and stress. However, it has yet to be evaluated in patients with long-term respiratory conditions. Our group has recently received funding to explore and develop personalised 'disease specific' psychological interventions for people with asthma (BA: SPCR Postdoctoral Fellowship Award) and the matched-funding opportunity provided by Headspace will allow an assessment of recruitment response rate, intervention retention, outcome measure feasibility (see below) and variability within outcomes in order to support a definitive trial.

120 consenting volunteers will complete validated and widely used measures of control and disease-specific quality of life (including the Asthma Control Questionnaire and Asthma Quality of Life Questionnaire) as well as questionnaire measures of mindfulness using validated questionnaire tools before and after taking part in the Headspace course (or before and after treatment as usual in the control group: 80vs.40). The course consists of 8 'sessions' lasting 10 minutes, in which users listen to a guided meditation practice. The course is available on computer and on mobile devices; users are able to listen to each session as many times as they want, with a new session being unlocked each day.

Alongside the primary quantitative analysis (recruitment, retention & response rate) participants will also be invited to take part in telephone-based qualitative interviews that will discuss their experiences of taking part (for example, were there any barriers that hindered intervention usage) and the acceptability of the intervention (can the intervention be improved for use in a specific asthma population). Further investigation will also examine the extent to which Headspace usage analysis is associated with symptom improvement – particularly measures of intervention engagement and adherence, and whether they could be improved and exploration of barriers and facilitators for a subsequent fully powered randomised controlled trial.

# Additional exploratory hypotheses

- 1. Patients in the intervention group will show improvements in measures of anxiety and asthma-specific quality of life (vs. control group).
- 2. Improvements in anxiety and asthma-specific quality of life will be associated with changes in self-reported mindfulness.

## Design

This will be a randomised between-groups feasibility trial, using pre-post testing to assess recruitment response rate as well as exploratory analysis of within-subject impact of the intervention vs control (usual treatment).

## Sample population and recruitment

120 eligible patients will be identified by their GP practices using specified inclusion and exclusion criteria to search the GP electronic patient database. If deemed eligible by the GP they will be invited to take part in the study via a letter from the GP (sample size enables detection of 20% response rate with confidence interval of

 $\pm$ 7%, to accurately inform a randomized controlled trial for an intervention with a similar target population). GP practices will also have the option to use Docmail to help with the mail out if they prefer. There may also be opportunistic recruitment by GPs and community pharmacists with leaflets and posters about the study being on display. There will also be the opportunity to put information about the study on the GPs website, electronic visual displays at the surgery or on the surgery website or their social media page if they wish (using the electronic version of the poster).

Recruitment will take place with the help of Wessex CRN (estimate of costings attached). We will contact approximately 6-10 GP services who are interested in taking part in the study. We will aim to recruit a spread of GP practices across both urban and rural locations with different socio-economic qualities and deprivation scores.

Given the nature of this research as a well-powered feasibility study, we will not aim to balance study recruitment across age, gender, and ethnicity but will explore this in post-hoc analysis. We will, however, purposively sample across age, gender, asthma severity and ethnicity in the qualitative process analysis.

Patients will be selected as meeting the eligibility criteria below by their GP, and will be posted a copy of the participant information sheet and details of how to sign up to the study online, along with email contact details of the study team should they have any further queries.

Participants will also be sent an optional freepost reply-form to send back to the study team should they not wish to take part with the option to provide some demographic details and a reason for declining to take part in the study. It will be made clear that this is optional and it is up to the participant whether they wish to send this information back to the research team.

Inclusion criteria: Patients will be: adult (18 years or over), with a confirmed diagnosis of asthma, between steps 2 and 4 of BTS Asthma Guidelines for symptom severity (mild to moderate). They will also need access to the Internet which can be either computer mobile device. а or а *Exclusion criteria:* Patients will be excluded from the study if they are under 18 years of age, have previously diagnosed major and unstable comorbid psychological disorders other than anxiety / depression, have current participation in another asthma intervention study or have had acute exacerbation of asthma (needing a course of oral steroid of increased dose of maintenance steroids) within the previous 28 days.

Participants who sign up online will enter the study website, created in the University of Southampton Lifeguide platform. Consent will be taken online and patients will then complete brief demographic information (age, gender, education, ethnicity, and work & health status) and confirm inclusion and exclusion criteria. The Lifeguide platform will automatically confirm eligibility. Non-eligible participants (based on inclusion/exclusion criteria) will be informed that they are not eligible to take part in the study and that they can contact the study team if they would like their data to be removed.

Eligible patients will complete the baseline questionnaire measures before being randomised to intervention or control using the automatic randomisation function within the LifeGuide platform. Most questionnaire measures are envisaged to be administered online but there may also be the option to complete postal paper versions if the situation arises that might require this option. Participants in the intervention group will be enrolled on to the online mindfulness course.

This sample size is well within a feasible recruitment estimate according to patient characterization (estimates of anxiety/depression comorbidity between 16 and 52 %) and our study teams' experience of recruiting patients with asthma through local GP services.

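### The ±7% precision for the response rate leaves out variation between the 6-10 GP practices, and whether it is too narrow depends on how many patients are invited

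*Protocol*

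**What the plan says.** The precision claim is in the Protocol, section Sample population and recruitment: "sample size enables detection of 20% response rate with confidence interval of" plus or minus "7%, to accurately inform a randomized controlled trial for an intervention with a similar target population". No confidence level, ICC or design effect accompanies it.

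The same section describes how patients are reached. It begins "120 eligible patients will be identified by their GP practices" and continues "If deemed eligible by the GP they will be invited to take part in the study via a letter from the GP". On the number and kind of practices it says "We will contact approximately 6-10 GP services who are interested in taking part in the study" and "We will aim to recruit a spread of GP practices across both urban and rural locations with different socio-economic qualities and deprivation scores". It also allows opportunistic recruitment through GPs, pharmacists, posters, websites and social media.

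Elsewhere 120 is the number taking part. The Summary says "120 consenting volunteers will complete validated and widely used measures of control and disease-specific quality of life", and the Outline and Lay Summary split that number 80 to 40. The Summary and the Design section make response rate a main feasibility outcome.

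**The concern.** Patients are identified, screened and invited by their own practice, so invitees come in clusters. Response can vary by practice with the list, the population served and the way the mail-out is handled. The rate is meant to inform a later trial. Unless that trial uses the same practices, variation between practices is part of the error in carrying the rate forward. A formula that treats all invitees as independent sets this component to zero.

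If the component matters, the later trial's number of practices and letters would be planned with more certainty about recruitment than the data give. How far this affects the printed ±7% depends on whether 120 is the number invited or the number consenting, and the protocol uses it as both.

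**Working it through.** **Inputs.** From Sample population and recruitment: rate p = 0.20, stated half-width 7 points, N = 120 invited, k = 6 to 10 practices. From the Summary: 120 consenting, which at a 20% response means 120/0.20 = 600 invited. Assumed, because the protocol gives neither: a two-sided 95% level, and an ICC of 0.01-0.05. At p = 0.20 that ICC range corresponds to a between-practice SD of sqrt(0.01 × 0.16) = 4 points to sqrt(0.05 × 0.16) = 9 points. Practices are taken to be of equal size.

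**Step 1: reproduce the plan's figure.** 1.96 × sqrt(0.2 × 0.8/120) = 0.0716, or ±7.2 points. A 90% level gives ±6.0, which does not match. So ±7% is the unclustered 95% half-width for n = 120.

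**Step 2: add practice.** With m = N/k, the design effect is DE = 1 + (m − 1) × ICC, and the half-width is 1.96 × sqrt(0.16 × DE/N). Each cell shows DE and half-width in percentage points.

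| Invited | Practices | m | ICC 0.01 | ICC 0.02 | ICC 0.05 |
|---|---|---|---|---|---|
| 120 | 10 | 12 | 1.11; ±7.5 | 1.22; ±7.9 | 1.55; ±8.9 |
| 120 | 6 | 20 | 1.19; ±7.8 | 1.38; ±8.4 | 1.95; ±10.0 |
| 600 | 10 | 60 | 1.59; ±4.0 | 2.18; ±4.7 | 3.95; ±6.4 |
| 600 | 6 | 100 | 1.99; ±4.5 | 2.98; ±5.5 | 5.95; ±7.8 |

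Without clustering, 600 invited would give 1.96 × sqrt(0.16/600) = ±3.2.

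**Step 3: at what ICC does ±7 fail with 600 invited?** Set 3.2 × sqrt(DE) = 7. Using the unrounded half-width, DE = (0.07/0.03201)² = 4.78. The ICC is then 3.78/99 = 0.038 with 6 practices and 3.78/59 = 0.064 with 10. With 120 invited there is no such threshold, since 7.16 already exceeds 7 slightly and any positive ICC widens it.

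**Step 4: coverage.** This was simulated with 100,000 beta-binomial samples per case.

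- 120 invited, nominal 95% binomial interval: 92%, 90% and 83% with 6 practices and 93%, 92% and 88% with 10, for ICC 0.01, 0.02 and 0.05.
- 600 invited, interval of ±7 points: 98.8-99.9% for ICC 0.01-0.02; at ICC 0.05, 97.2% with 10 practices and 92.7% with 6.
- A t interval on practice-level rates covered about 94-95% in every case.

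**Step 5: few clusters.** With a t quantile on k − 1 degrees of freedom, the half-widths for 120 invited run from ±8.7 (10 practices, ICC 0.01) to ±13.1 (6 practices, ICC 0.05). Much of that is the quantile itself: at ICC 0 the same formula gives ±8.3 with 10 practices and ±9.4 with 6. For 600 invited the range is ±4.7 to ±10.2, so with t the thresholds in step 3 would be lower.

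**The case against.** The strongest reply is that the protocol mostly treats 120 as the number of participants. About 600 are then invited, and ±7 points is wide enough over most of the assumed ICC range. This stands, and it limits the point.

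A reader might go further and infer that the stated interval is too narrow whatever the denominator. The documents do not support that, as steps 3 and 4 show. A reader might also note that a binomial interval on 600 (±3.2) would cover only 58-88% over the same ICC range. That is true of such an interval, but the protocol neither states nor plans one, so it is no evidence against ±7%.

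Three further replies have weight.

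- The ICC is an assumption. At 0.01 with 120 invited the loss is under 1 point.
- Aiming for a spread of settings does not show that response rates differ between practices. A spread resembles stratification and could even steady the overall rate. No variation in response is documented.
- The choice of interval method may properly sit in an analysis plan that is not shown, and its absence from the protocol is not held against it.

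What remains is that ±7% is printed in the protocol as the reason for the size, and it assumes zero variation between practices on either reading of 120.

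**Conclusion.** The concern holds in a conditional form. The stated ±7% is the simple-random-sample figure for n = 120 and omits variation between practices. The arithmetic itself is correct; the independence assumption behind it is what does not fit the design.

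- **120 invited (literal reading):** optimistic for any positive ICC, with a half-width of about ±7.5 to ±10.0 for an assumed ICC of 0.01-0.05.
- **120 consenting, about 600 invited:** about ±4.0 to ±7.8. Using the normal quantile, ±7% is too narrow only above an ICC of about 0.038 (6 practices) to 0.064 (10 practices).

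These figures rest on a 95% level, equal practice sizes and an ICC range that the protocol does not supply. The unclear denominator is the larger fault in the sentence, since 20% of 120 invited would yield only 24 participants. Correcting the denominator alone would still leave the practice component out. The protocol ties no progression threshold or mail-out calculation to this interval, so the effect on the later trial is a risk to its planning and not a demonstrated error.

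**What to change.** In Sample population and recruitment:

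- State the number invited as the denominator, and the confidence level.
- Replace ±7% with a half-width that includes the design effect 1 + (m − 1) × ICC, shown over a stated ICC range.

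For reporting, in Data analysis or the analysis plan:

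- Give the response rate to mailed invitations with an interval that treats the practice as the sampling unit, for example t on practices minus 1, together with the practice-specific rates.
- Count sign-ups from posters, pharmacies, websites and social media separately, because they have no invitation denominator.

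At sign-up, record each responder's practice. It is not among the demographic items the protocol lists, and practice-level rates cannot be formed without it.

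The cost is wording, a short analysis, one extra sign-up item and a less favourable stated precision. No extra patients or visits are needed.

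### The aim names sub-optimally controlled asthma and the summary adds anxiety, but no entry criterion selects on either

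*Protocol*

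**What the plan says.** The Aim section targets "a digital mindfulness-based stress-reduction app, in patients with sub-optimally controlled asthma". The Summary opens with a narrower group: "We are examining the use of 'mindfulness' training for people with poorly controlled asthma (PCA) and anxiety". The Lay Summary and Outline speak only of patients with asthma.

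The eligibility list, under Sample population and recruitment, asks for age 18 or over, a confirmed asthma diagnosis, internet access and a treatment step "between steps 2 and 4 of BTS Asthma Guidelines for symptom severity (mild to moderate". It excludes major unstable psychological disorders other than anxiety or depression, concurrent participation in another asthma intervention study, and an acute exacerbation in the previous 28 days. LifeGuide confirms eligibility, and eligible patients then complete the baseline questionnaires before randomisation. Data collection lists the ACQ and HADS among those questionnaires.

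The same section calls the sample size feasible partly because of "estimates of anxiety/depression comorbidity between 16 and 52" per cent. The Outline plans to examine recruitment, retention and response rate and the "degrees to which these differ from the in-person mindfulness intervention delivered in the MIDAS study" (SPCR ref 273). The Summary places the work under that reference number among "patients attending the 'difficult asthma' clinic in Southampton".

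**The concern.** Three parts of the protocol describe three different groups: sub-optimal control (Aim), poor control plus anxiety (Summary), and any asthma at BTS steps 2-4 (entry criteria). A well-controlled patient without anxiety meets every written criterion.

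The study's main products are recruitment, retention, response and outcome variability, which are meant to support a definitive trial. If they are reported under the heading of sub-optimally controlled asthma, they will be attributed to a population that was not selected. A later trial that did restrict entry on control would inherit rates from a broader group. The comorbidity range raises the same problem: it can affect how many people are recruitable only if comorbidity is required, and it is not.

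**Working it through.** **Does any criterion select on control or anxiety?**

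| Feature | Aim | Summary | Entry criteria |
|---|---|---|---|
| Asthma control | sub-optimal | poor | not mentioned |
| Anxiety | not mentioned | named | permitted, not required |
| BTS step | not mentioned | not mentioned | 2-4, labelled mild to moderate |
| Recent exacerbation | not mentioned | not mentioned | excluded if within 28 days |

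The BTS step is presented as a measure of severity and sets no control threshold. The 28-day exclusion removes some recently unstable patients, so it does not enforce poor control either. The ACQ and HADS come after the eligibility check, so they do not gate entry.

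**The plan's own precision figure.** Inputs are n = 120 and a 20% response rate, both from Sample population and recruitment. The confidence level is not stated, and 95% two-sided is assumed. Half-width = 1.96 × √(0.20 × 0.80 / 120) = 0.0716, or ±7.2 points. The stated ±7% is reproduced and is not in dispute.

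**Anxiety or depression among enrolees**, assuming the cited 16-52% carries over to them:
- 0.16 × 120 = 19.2 and 0.52 × 120 = 62.4, so about 19 to 62 of 120.
- By arm: about 13 to 42 of 80, and 6 to 21 of 40.
- Without either condition: about 58 to 101 of 120.

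**Sub-optimal control among enrolees.** The protocol gives no figure. The range 30% to 70% is assumed for illustration only.
- 0.30 × 120 = 36 and 0.70 × 120 = 84 target patients.
- For a 20% proportion estimated among those patients alone (for instance an attrition rate), the half-width is 1.96 × √(0.16 / 36) = ±13.1 points or 1.96 × √(0.16 / 84) = ±8.6 points, against ±7.2 for all 120.

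**Otherwise eligible volunteers needed for 120 if a criterion were added:**
- Sub-optimal control required (assumed share 70% to 30%): 120 / 0.70 = 172 to 120 / 0.30 = 400.
- Anxiety or depression required (share 52% to 16%): 120 / 0.52 = 231 to 120 / 0.16 = 750.

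**Response rate in the target group.** This needs the number of invited patients who are sub-optimally controlled. Only people who sign up and pass eligibility complete the ACQ and HADS. Those who decline may return an optional form with some demographic details and a reason. The denominator is therefore unknown, and the rate cannot be computed.

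**MIDAS.** The shared reference number ties MIDAS to the difficult-asthma clinic. This trial identifies patients through GP practices, with opportunistic recruitment by GPs and community pharmacists. Population and setting therefore differ along with the mode of delivery.

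**The case against.** The best defence is that this is a feasibility study. Effects on outcomes are exploratory, and the criteria exclude no poorly controlled patient at steps 2-4. The ACQ and HADS are collected at baseline, and Data analysis allows regression that adjusts for baseline traits, so case mix can be described afterwards. This stands in part. Retention, usage and variability can be tabulated for the sub-optimally controlled subset with less precision. The mailed response rate cannot be, and describing case mix does not align the aim with the criteria.

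It is also fair that anxiety appears in the Summary and not in the Aim, so the conflict over control is the stronger one. The 16-52% range comes from a cited source and may not fit volunteers for a mindfulness study.

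A reader might infer more than the protocol shows:
- **That the sample will be a milder population.** The label mild to moderate refers to severity, and the control mix of enrolees is unknown.
- **That the trial cannot answer its aim.** Target patients are eligible and can be identified from the baseline ACQ.
- **That a treatment effect will be diluted by a known amount.** Any such figure needs an effect size, a well-controlled share and an assumption of no benefit in those patients. The protocol supplies none of these, and efficacy is exploratory.
- **That the protocol credits digital delivery with any difference from MIDAS.** It proposes only to examine how far the rates differ.

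**Conclusion.** The inconsistency is real, and no other part of the protocol resolves it. As written, the trial would attach conclusions about sub-optimally controlled asthma to a sample not selected for control, and the Summary's mention of anxiety has no counterpart at entry. The supportable statement is that the sample will include an unknown share of patients outside the stated target.

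For anxiety or depression, the expected number is about 19-62 of 120, conditional on the cited range applying to enrolees. For control, no figure follows from the protocol; the 36-84 of 120 shown above rests on an assumed 30-70%. The comorbidity range does not bear on recruitment under the present criteria. The comparison with MIDAS is confounded by population and setting, and a control criterion at entry would not remove the difference in setting.

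**What to change.** Reconcile the Aim, the Summary and the entry criteria before recruitment starts.

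**Lower-cost route: keep entry as it is.**
- Restate the Aim and Summary as adults with asthma at BTS steps 2-4.
- Remove the comorbidity range as support for the recruitment estimate.
- Report the share of enrolees who are sub-optimally controlled on the ACQ and anxious on the HADS, at cut-offs the sponsor chooses in advance.
- Report retention, usage and the AQLQ and HADS results by baseline ACQ band.
- State that the mailed response rate applies to all invited step 2-4 patients and cannot be given for the target subgroup.

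This costs wording and a few tables on data already collected. The drawback is wider intervals within bands.

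**Alternative: keep the aim.** The sponsor would then need a control criterion at entry, and would have to decide whether anxiety is also meant to be required. The recruitment estimate would need revision: about 172-400 otherwise eligible volunteers for 120 enrolees if the sub-optimally controlled share is 70-30% (assumed). This is a trade-off for the sponsor to weigh.

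**Under either route,** describe the Outline's comparison with MIDAS as confounded by population and setting. That costs one sentence.
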